The removal of third molars is one of the most frequently performed procedures in dentistry, and can be carried out in a hospital setting under general anesthesia. In such cases, local anesthetics are often administered at the surgical site in addition to general anesthesia, to promote better hemostasis and postoperative analgesia. Bupivacaine is a local anesthetic commonly used in these situations. However, its known cardiotoxic and neurotoxic effects, as reported in the literature, have led to increased interest in safer alternatives, such as ropivacaine. **Objective:** to evaluate whether there is a significant difference between bupivacaine and ropivacaine in terms of postoperative analgesic efficacy, intraoperative hemostasis, and patient vital signs during the intraoperative period. **Materials and Methods:** This was a randomized, controlled, split-mouth clinical trial. The sample size was based on a similar previously published study and included 15 participants ($n = 30$). As this study also follows a split-mouth design, each of the 15 patients underwent two tooth extractions. All patients had indications for the removal of both lower third molars under general anesthesia. Surgical extractions were performed in a single session, with bupivacaine (Group A) administered at one surgical site and ropivacaine (Group B) at the other. The procedures were carried out at the Hospital de Clínicas de Porto Alegre. Vital signs were continuously monitored by the same anesthesiology team, with data collected at the time of drug injection (before and immediately after), as well as one minute and five minutes post-injection. Intraoperative bleeding was measured by calculating the volume of blood aspirated into the collection vial, from the time of incision to the final suture, at each surgical site. To minimize systemic interference from the anesthetic agents, their administration was alternated between patients. Postoperative analgesia was self-reported by the patients using a Visual Analog Scale (VAS) for each side at various postoperative time points. A descriptive analysis will be conducted on the clinical data obtained through these measurements.

Key-words: Third Molar; Anesthetics, Local; Surgery, Oral

SUMÁRIO

SUMMARY	5
1 INTRODUCTION	6
2 LITERATURE REVIEW	8
3 OBJECTIVES	10
4 METHODOLOGY	11
4.1 ETHINCAL ASPECTS	11
4.2 TYPE OF STUDY	11
4.3 LOCATION	12
4.4 SAMPLE	12
4.5 PREOPERATIVE CONDUCTS	13
4.6 SURGICAL TECHNIQUE	13

1 INTRODUCTION

The search for painless surgical interventions was a highly controversial topic just a few centuries ago, often considered a utopia or the work of charlatans. This panorama began to change in the 18th century with the discovery of the anesthetic properties of nitrous oxide, known as "laughing gas," culminating in the first surgery performed under general anesthesia in October 1846.¹ Since then, new anesthetic agents have been developed and introduced into medical practice.²

General anesthesia is an anesthetic technique in which a combination of drugs is used to induce analgesia, unconsciousness, immobility, and skeletal muscle relaxation, allowing procedures to be performed with greater safety and comfort for both professionals and patients.³ Currently, general anesthesia can be achieved using intravenous or inhaled agents, or a combination of both. Anesthetic agents widely used in Brazil include thiopental, propofol, etomidate, and midazolam (intravenous) and halothane, isoflurane, and sevoflurane (inhalation).⁴

In dentistry, general anesthesia has several indications and can be used in cases of extensive or highly complex surgical procedures, in patients with odontophobia or extreme anxiety, in patients with special needs or children who cannot be managed in the office, and in patients allergic to local anesthetics, among other situations. Despite this, the use of general anesthesia in dentistry is not routine for most Brazilian dentists. On the other hand, local anesthetics are the most widely used and prevalent substances in dentistry, and their use is essential for adequate clinical practice.⁵ They are defined as substances capable of reversibly blocking nerve conduction by inhibiting the excitation and conduction processes of the nerve cell membrane, resulting in temporary impairment of thermal, pain, and tactile sensitivity without causing loss of consciousness.⁶ Currently, the use of local anesthetics in dentistry is considered quite safe, with substances that have low systemic toxicity, are non-irritating to tissues, and do not cause permanent nerve damage, ideally offering a short onset of action and sufficient duration for surgical procedures.⁷

The most commonly used local anesthetics in dentistry are amide-type agents, including lidocaine, prilocaine, mepivacaine, articaine, bupivacaine, ropivacaine, and levobupivacaine.^{5,7}

Lidocaine hydrochloride, the most widely used amide-type local anesthetic in dentistry, is considered very safe for pregnant women, children, and heart patients.

Commercial preparations containing lidocaine are diverse and may or may not be combined with vasoconstrictors such as epinephrine, norepinephrine, and phenylephrine.⁸

Prilocaine hydrochloride has a structure very similar to lidocaine, but is less potent and less toxic. It is often found in commercial formulations combined with felypressin, exhibiting minimal cardiotoxicity. Its use is contraindicated in patients with methemoglobinemia, anemia, or hypoxic heart failure.⁹ Felypressin is contraindicated in pregnant women due to its potential to cause uterine contractions.¹⁰

Mepivacaine hydrochloride is approximately twice as potent and toxic as lidocaine and is often used in combination with levonordefrin, norepinephrine, or epinephrine. However, unlike lidocaine, its use without an associated vasoconstrictor has clinical relevance, with an anesthetic effect lasting 20 to 40 minutes, significantly longer than the 5 minutes of lidocaine without a vasoconstrictor. It is an excellent choice for cases where the use of vasoconstrictors is contraindicated.¹¹

Articaine hydrochloride, the most widely used local anesthetic in countries such as Germany and the United States, is often found in combination with epinephrine. It has greater potency and less toxicity than lidocaine. It is contraindicated in patients with methemoglobinemia, anemia, or hypoxic heart failure.¹² Despite reports of paresthesia associated with the use of articaine, there is no high-quality scientific evidence to support this relationship.¹³

Bupivacaine hydrochloride provides long-lasting anesthesia, significantly contributing to the reduction of postoperative pain, and is the most widely used anesthetic in dental procedures under general anesthesia in hospital settings. Its potency is considerably greater than that of the other anesthetic agents mentioned above. However, its onset of action is slower, taking about 6 to 10 minutes to initiate analgesia. It can be used without vasoconstrictors or in combination with epinephrine.^{11,14} The cardiotoxicity of bupivacaine is well documented, with cardiovascular collapse being widely reported, especially when erroneously applied intravascularly, and it is difficult to reverse.¹⁵

As a result, there has been a search for a new anesthetic substance that combines the advantages of bupivacaine (high potency and long duration) while minimizing its disadvantages (lower cardiac toxicity and arrhythmogenic properties). Among the substances found, levobupivacaine and ropivacaine stand out.¹⁶

Levobupivacaine hydrochloride shares properties with racemic bupivacaine, but

with lower cardiac toxicity. Its use is more common in the medical field, often combined with epinephrine. However, its use is not widespread in dentistry.¹⁷

Ropivacaine hydrochloride also has properties similar to racemic bupivacaine, but with reduced cardiac toxicity. Furthermore, it has intrinsic vasoconstrictor properties, minimizing the need for additional vasoconstrictors during its administration.^{16,18}

Among the main benefits of using local anesthetics are comfort, analgesia, vasoconstriction (when combined with vasoconstrictors) and reduce postoperative pain, what makes its use is recommended even during procedures under general anesthesia.¹⁹ Even with the proven greater safety of anesthetic agents such as levobupivacaine and ropivacaine, bupivacaine still dominates hospital dental practice, despite so much evidence against its use.²⁰ Moreover, there is no protocol or commercial formulation for its use in anesthetic tubes, further hindering the use of these alternative anesthetic agents in dentistry. Therefore, this study aims to evaluate whether there is a significant difference between bupivacaine and ropivacaine in terms of postoperative analgesia, intraoperative hemostasis, and the patient's vital signs during the procedure.¹⁶

2 LITERATURE REVIEW

2.1 RACEMIC BUPIVACAINE

Bupivacaine is a potent local anesthetic from the amide group, widely used in regional anesthesia, epidural anesthesia, spinal anesthesia, and local anesthesia. It is available in three different concentrations: 0.25%, 0.5%, and 0.75%.²¹ It is called racemic because it is an equimolar mixture of dextrorotatory and levorotatory isomers.²² Bupivacaine has a slow onset of action (6 to 10 minutes), a half-life of 2.7 hours, and intrinsic vasodilatory potential. It is commonly used in more extensive procedures that require prolonged intraoperative and postoperative anesthesia.¹¹ To reduce intraoperative bleeding, toxicity, and the required dose for anesthesia, vasoconstrictors are frequently added to bupivacaine, with epinephrine being one of the most commonly used substances.²³

Bupivacaine was first synthesized in 1957 and introduced to the market in the mid-1960s. As its use increased, so did reports of adverse effects, including toxicity to the central nervous system and cardiovascular system.²⁴ Bupivacaine is closely associated with seizures, severe bradycardia, and cardiac arrest, which are often

resistant to conventional cardiopulmonary resuscitation techniques.²⁵ These side effects are frequently linked with overdose or accidental intravascular injection.²⁶

Duo to these concerns, several studies have been conducted to better understand the cause of bupivacaine's toxicity, ultimately leading to the exploration of isomers and the development of new anesthetic agents.²⁷

2.2 LEVOBUPIVACAÍNE

Levobupivacaine is a long-acting anesthetic agent developed in response to reports of toxicity associated with bupivacaine in the 1970s.²⁸ It is a pure enantiomer of bupivacaine, composed exclusively of levorotatory isomers, which explains its distinct physiological effects, despite the molecules being very similar.²⁷ This local anesthetic has several properties that distinguish it from racemic bupivacaine, including less associated vasodilation, longer duration of action, lower potency, and reduced toxicity to the central nervous system and cardiovascular system.²⁹

2.3 ROPIVACAINE

Ropivacaine was also developed in response to reports of toxicity associated with bupivacaine, becoming commercially available only in the mid-1990s.²⁴ Although its name does not specifically mention levorotatory isomers, ropivacaine is, in fact, a pure levorotatory version, similar to levobupivacaine.²⁷

It is a long-acting amide-type local anesthetic with slightly lower potency and duration of action compared to bupivacaine, exhibiting rapid dissociation from sodium channels, which contributes to its reduced cardiotoxicity.^{30, 31, 32} Furthermore, animal studies show that resuscitation after local anesthetic-induced cardiovascular collapse was more easily achieved in the ropivacaine group compared with the bupivacaine group.³³

Studies indicate that higher doses of ropivacaine are required to trigger symptoms and initial signs of toxicity in the cardiovascular and nervous systems when compared with racemic bupivacaine.³⁴ Unlike most local anesthetics, ropivacaine possesses intrinsic vasoconstrictor properties, which may be beneficial in surgical practice.^{35, 36}

3 OBJECTIVES

3.1 GENERAL OBJECTIVE

This study aims to evaluate whether there is a significant difference between 0.5% bupivacaine with 0.2MI of epinephrine and 0.75% ropivacaine with 0.2MI of epinephrine in terms of postoperative analgesic capacity, intraoperative hemostasis and the patient's vital signs during the transoperative period.

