3.2 SPECIFIC OBJECTIVES

- Measure the amount of intraoperative bleeding (in mL) during procedures performed with 0.5% bupivacaine with 0.2 mL of epinephrine and 0.75% ropivacaine with 0.2 mL of epinephrine.
- Assess potential changes in patients vital signs during and after the administration of local anesthetics.
- Compare the levels of postoperative discomfort associated with anesthetic agents using a visual analog scale (VAS).

JUSTIFICATION

Despite the well-known cardiotoxic and neurotoxic effects of bupivacaine, it continues to be widely used in oral and maxillofacial surgery. This study aims to compare and evaluate the feasibility of using a less toxic anesthetic agent in lower third molar removal surgeries under general anesthesia.

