4.1 SAMPLE CALCULATION

The sample size was determined for convenience, based on a similar study previously conducted³⁷, which established a significance level of 5% ($p < 0.05$), a power of 80%, and a 5% margin of error for its calculation ($n = 30$). In the baseline study, a comparison was made between ropivacaine and lidocaine during implant placement, with procedures performed on 15 patients, as it was a split-mouth design. In the present study, procedures will be performed on 15 patients, yielding a total sample size of 30.

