4.10 DATA ANALYSIS

A descriptive analysis will be performed on the changes in vital signs observed during the operation (if any). A direct comparison and calculation of the averages will be made between the values observed in both the postoperative analgesia evaluation and the transoperative bleeding assessment.

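### The rationale is substitution, but section 4.10 compares bare averages from 15 pairs, so similar averages or a non-significant result could not by themselves support equal analgesia

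*Protocol*

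**What the plan says.** Three parts of the protocol bear on this point.

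- **Purpose.** The Introduction takes the safety advantage as settled: "Even with the proven greater safety of anesthetic agents such as levobupivacaine and ropivacaine, bupivacaine still dominates hospital dental practice". The Justification after section 3.2 says the study aims to "compare and evaluate the feasibility of using a less toxic anesthetic agent". Section 2.3 describes ropivacaine as having "slightly lower potency and duration of action compared to bupivacaine".
- **Objective.** Section 3.1 sets out to "evaluate whether there is a significant difference between 0.5% bupivacaine" and ropivacaine, each with epinephrine, in analgesia, hemostasis and vital signs. No non-inferiority or equivalence hypothesis and no margin appears anywhere.
- **Analysis.** For pain and bleeding, section 4.10 says: "A direct comparison and calculation of the averages will be made between the values observed". It names no test and no interval. Vital signs are to be described only.

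Section 4.1 (Sample Calculation) sets the size at 15 patients for convenience. It follows an earlier split-mouth study of ropivacaine against lidocaine in implant surgery, which is said to have used a 5% significance level, "a power of 80%, and a 5% margin of error for its calculation". It gives no effect size, SD or margin.

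**The concern.** If the safety of ropivacaine is taken as given and its analgesia is expected to be a little weaker, the practical question for pain is whether any loss is small enough to accept. A question about a significant difference does not answer that, and neither does a comparison of two averages. The result most convenient for the substitution argument is that no difference is found, and that result becomes more likely as the trial gets smaller and noisier.

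At stake is the conclusion drawn from similar averages. Without an interval, a reader cannot tell whether the data rule out an important loss of pain control or only fail to show one. The protocol gives no rule for reading such a result.

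**Working it through.** **The plan's own figure.** The 15 patients (30 sites) cannot be reproduced, because section 4.1 gives no effect size, SD or margin. At two-sided 5% and 80% power, 15 pairs detect a difference of 0.78 SD of the paired difference. Counting 30 as pairs would give 0.53 SD. Reading the 5% margin of error as the precision of a proportion of 0.5 would need 385 observations. None of these recovers a stated target.

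**Inputs.**
- n = 15 pairs (sections 4.1 and 4.2, split-mouth).
- Pain on a 0-10 scale for each side, at five time points (section 4.9).
- Significance level 5% (section 4.1, borrowed from the earlier study; two-sided is assumed).
- SD of the within-patient pain difference: not given. Values of 1.5, 2.0 and 2.5 points are assumed, for one time point or one summary per patient.
- True disadvantage of ropivacaine: 1 point, assumed for illustration.

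**Precision.** The half-width of the 95% interval is t(0.975, 14) × SD / √15, and 2.145 / 3.873 = 0.554, so it is 0.554 × SD.

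**Chance of missing a 1-point disadvantage.** For a two-sided 5% paired t-test, the noncentrality is (1 / SD) × √15 with 14 degrees of freedom.

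| Assumed SD | 95% half-width | Noncentrality | Power | Non-significant |
|---|---|---|---|---|
| 1.5 | 0.83 | 2.58 | 0.671 | 33% |
| 2.0 | 1.11 | 1.94 | 0.438 | 56% |
| 2.5 | 1.38 | 1.55 | 0.303 | 70% |

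**What an observed difference of zero would show.** It excludes a 1-point disadvantage only if 0.554 × SD is below 1, that is, if the SD is below 3.873 / 2.145 = 1.81 points.

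**Bleeding.** The same standardised half-width of 0.55 SD applies to the paired difference in mL. The protocol gives no SD in mL, so no absolute figure can be stated.

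**The case against.** The strongest reply has five parts.

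- **No test is planned.** A reader might infer from section 3.1 that the trial tests for a difference and will report a null result as equality. The documents do not support this. Section 4.10 plans averages only, and nothing says how a null result will be read. This part stands, so the miss rates above apply only if a paired test is used. The half-width does not depend on a test and shows what the averages leave out.
- **A difference objective is legitimate.** It is two-directional and, with an interval, could show ropivacaine to be worse. This also stands. The gap is the missing interval and the missing rule for reading it.
- **Bleeding is different.** The Introduction and section 2.3 say that ropivacaine constricts vessels by itself, and section 2.1 says that bupivacaine tends to dilate them. That is a real reason to look for a difference in hemostasis, so bleeding should not be recast as a non-inferiority question.
- **A compulsory margin is a debatable trade-off at this size.** With an illustrative 1-point margin, one-sided 2.5% and no true difference, 15 pairs have 67%, 44% or 30% power for SDs of 1.5, 2.0 or 2.5. Reaching 80% would need 20, 34 or 52 pairs. Shared systemic analgesia may also lower scores on both sides, which would make a raw margin easier to meet. This is why a margin is optional in the fix.
- **A statistical analysis plan may supply intervals.** It may, and none is at hand. The mismatch between rationale, objective and stated analysis is nevertheless in the protocol itself.

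**Conclusion.** The point holds in a limited form. The rationale is substitution, the objective asks about a significant difference, and the stated analysis gives averages without uncertainty. Followed as written, it can neither establish a difference nor support acceptable similarity.

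For pain, the estimate would carry an uncertainty of about 0.83 to 1.38 points either way. A true 1-point disadvantage could go undetected in 33% to 70% of trials if a paired test were used. These figures rest on assumed SDs of 1.5 to 2.5 points and an assumed 1-point difference. The multiple 0.55 SD rests only on 15 complete pairs.

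The documents do not show that the trial must become a non-inferiority trial for both outcomes, or that its authors intend to claim equality from a null result. They leave that reading open, and a small change would close it.

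**What to change.** - In section 4.10, replace the comparison of averages for pain and bleeding with the mean within-patient difference (ropivacaine minus bupivacaine) and its 95% confidence interval.
- State that a small or non-significant difference will not be described as similar or equal unless the interval excludes a difference the team considers important. Otherwise the result is reported as inconclusive.
- For pain, the team may fix that difference as a margin before examining the data. The Summary already describes the procedures in the past tense, so if data have been seen, the report should say that the margin was set afterwards.
- For bleeding, keep the difference objective.

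The cost is a change of wording and, if a margin is used, one clinical decision by the team. No extra patients or procedures are needed. The downside is that the trial may have to report an inconclusive result. If the team wants a firm non-inferiority conclusion on pain, it would also have to revisit the sample size.

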3.2 SPECIFIC OBJECTIVES

- Measure the amount of intraoperative bleeding (in mL) during procedures performed with 0.5% bupivacaine with 0.2 mL of epinephrine and 0.75% ropivacaine with 0.2 mL of epinephrine.
- Assess potential changes in patients vital signs during and after the administration of local anesthetics.
- Compare the levels of postoperative discomfort associated with anesthetic agents using a visual analog scale (VAS).

JUSTIFICATION

Despite the well-known cardiotoxic and neurotoxic effects of bupivacaine, it continues to be widely used in oral and maxillofacial surgery. This study aims to compare and evaluate the feasibility of using a less toxic anesthetic agent in lower third molar removal surgeries under general anesthesia.

4 MATERIALS AND METHODS

The study is designed as a randomized, controlled, split-mouth clinical trial. Patients receiving 0.5% bupivacaine with 0.2 mL of epinephrine are defined as group A (GA), while patients receiving 0.75% ropivacaine with 0.2 mL of epinephrine are classified as group B (GB).

4.1 SAMPLE CALCULATION

The sample size was determined for convenience, based on a similar study previously conducted³⁷, which established a significance level of 5% ($p < 0.05$), a power of 80%, and a 5% margin of error for its calculation ($n = 30$). In the baseline study, a comparison was made between ropivacaine and lidocaine during implant placement, with procedures performed on 15 patients, as it was a split-mouth design. In the present study, procedures will be performed on 15 patients, yielding a total sample size of 30.

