4.4 SAMPLE

The sample selection will consist of patients referred to the Oral and Maxillofacial Surgery Unit at the Hospital de Clínicas de Porto Alegre. The selected patients require bilateral extraction of lower third molars under general anesthesia, either due to the complexity of the surgery or due to systemic conditions that contraindicate local anesthesia. Patients who meet these criteria will follow the routine care protocol adopted by the team. During outpatient consultations, laboratory tests (including blood count, PT, aPTT, glucose, AST, ALT, and creatinine), imaging (CT scan of the skull and facial bones), and pre-anesthetic evaluation will be requested. If the tests are normal and cleared by the Anesthesiology team, patients will be placed on the waiting list and contacted when surgery is available. There will be no change to the routine care for patients volunteering in the study. The surgical procedures will be performed by the research team responsible for this study. The inclusion criteria will include patients aged 18 to 60, classified as ASA I or ASA II, who have impacted or semi-impacted lower third molars with similar positioning on both sides, according to the Pell and Gregory classification.³⁸

Patients who can undergo surgery under local anesthesia or who require additional procedures in the same surgical session, will be excluded from the sample. All patients, whether participating in the study or not, will have the right to withdraw from the study at any time without penalty.

Postoperative consultations will be conducted for follow-up, suture removal, and the evaluation and treatment of any potential postoperative complications.

Regarding general anesthesia, since this is a split-mouth study, both patients undergoing total intravenous anesthesia and general inhalational anesthesia will be included. Patients requiring additional intraoperative medications, which may interfere with the data, will be excluded. An example of this is patients receiving tranexamic acid during the procedure, as it could distort bleeding measurements between surgical sites.

The selection of the control group and experimental groups will be determined by a simple randomization in the immediate preoperative period. One surgical site will receive 0.5% bupivacaine + 0.2mL of epinephrine (GA) while the other site will receive 0.75% ropivacaine + 0.2mL epinephrine (GB).

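### Section 4.1 justifies the sample size with 80% power borrowed from a different comparison and reports 15 within-patient contrasts as a sample of 30; power for this trial is undetermined

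*Protocol*

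**What the plan says.** Section 4.1 of the protocol (Sample Calculation) opens with "The sample size was determined for convenience, based on a similar study previously conducted". The same sentence attaches that earlier study's settings: "which established a significance level of 5"%, then "a power of 80%, and a 5% margin of error for its calculation". Of the earlier study it says that "a comparison was made between ropivacaine and lidocaine during implant placement, with procedures performed on 15 patients", in a split-mouth design. For the present trial it concludes: "procedures will be performed on 15 patients, yielding a total sample size of 30".

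The Summary also gives 15 participants with n = 30, and explains that "each of the 15 patients underwent two tooth extractions".

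Section 4.4 (Sample) fixes the pairing: "One surgical site will receive 0.5% bupivacaine + 0.2mL of epinephrine (GA) while the other site will receive 0.75% ropivacaine". Every patient therefore contributes one site to each drug. The opening paragraph of section 4 nevertheless defines groups A and B as the patients who receive each drug.

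The General Objective asks whether the two drugs differ significantly in postoperative analgesia, intraoperative hemostasis and vital signs. None of these is linked to the sample size.

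**The concern.** Two things in section 4.1 do not fit this trial.

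First, the power. Power belongs to a specific outcome, difference, SD and test. An 80% figure set for one drug comparison in implant placement says nothing about another comparison in third-molar removal under general anesthesia unless those inputs are carried over, and none is.

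Second, the unit. Thirty is a number of surgical sites. The information about the drug difference comes from one contrast per patient, so the independent units are 15.

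At stake is how a null result is read. The protocol looks for a significant difference and, under Justification, wants to know whether a less toxic agent is feasible. If no difference is found, an 80% power and a sample of 30 in the sample-size section would make that finding look more conclusive than 15 pairs allow.

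**Working it through.** **Inputs from the protocol**
- Patients: 15 (section 4.1 and Summary).
- Sites per patient: 2, one per drug (section 4.4).
- Significance level 5% and power 80%: both reported as the earlier study's settings (section 4.1).
- Outcome used for sizing, difference, SD and within-patient correlation: not given, either for this trial or for the earlier study.

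**Assumptions made here**
- Two-sided paired t-test. The protocol names no test (section 4.10); two-sided fits an objective worded as a difference.
- Effects are expressed as δ = mean within-patient difference ÷ SD of the within-patient differences.

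**Step 1. The plan's own figures.** 15 patients × 2 sites = 30, so the stated 30 is reproduced, as a count of sites. The 80% power cannot be reproduced, because no effect or SD is given.

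**Step 2. Independent units.** One difference per patient gives n = 15 differences and 14 degrees of freedom.

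**Step 3. What 15 pairs detect.** Power = P(|T| > t(0.975, 14)), where T is noncentral t with 14 degrees of freedom and noncentrality δ√15, and √15 = 3.873.

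| True δ | Noncentrality δ√15 | Power with 15 pairs |
|---|---|---|
| 0.3 | 1.16 | 19% |
| 0.5 | 1.94 | 44% |
| 0.6 | 2.32 | 58% |
| 0.7 | 2.71 | 71% |
| 0.778 | 3.01 | 80% |
| 0.8 | 3.10 | 82% |
| 1.0 | 3.87 | 95% |

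Solving for 80% power gives δ = 0.778. The normal approximation, (1.960 + 0.842) ÷ 3.873 = 0.72, is slightly optimistic at this size. A one-sided 5% test would give 0.68.

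**Step 4. Precision.** The 95% confidence interval half-width is t(0.975, 14) ÷ √15 = 2.145 ÷ 3.873 = 0.55 SD of the differences.

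On the 0 to 10 VAS, the SD of within-patient differences is not in the protocol. For assumed values:

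| Assumed SD of differences (points) | 95% CI half-width (0.554 × SD) | Difference detectable at 80% power (0.778 × SD) |
|---|---|---|
| 1.5 | ±0.8 | 1.2 |
| 2 | ±1.1 | 1.6 |
| 3 | ±1.7 | 2.3 |

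**Step 5. Does counting 15 instead of 30 in itself reduce power?** If the 30 sites are misread as two independent groups of 15, the difference detectable at 80% power is 1.06 SD of the raw measurements. For 15 pairs with within-patient correlation ρ, it is 0.778 × √(2(1 − ρ)) raw SD:

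| ρ | Detectable difference (raw SD) |
|---|---|
| 0 | 1.10 |
| 0.25 | 0.95 |
| 0.5 | 0.78 |
| 0.75 | 0.55 |

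Setting this equal to 1.06 gives ρ = 1 − (1.06 ÷ 0.778)² ÷ 2 ≈ 0.07. Above that correlation, the paired count of 15 does at least as well as 15 versus 15 independent sites.

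**The case against.** The strongest reply is that the protocol makes no power claim for itself. It calls its size one of convenience and attributes the 5%, 80% and 5% figures to the earlier study. It also discloses 15 patients, explains the 30 by the split-mouth design, and describes the earlier study as having the same structure. All of that is correct.

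It rules out three stronger readings that a reader might infer:

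- **That the trial is shown to have less than 80% power.** The documents do not support this. With no outcome, effect or SD, power is undetermined: 15 pairs exceed 80% above 0.78 SD of the differences and fall short below it. Nor is 0.78 necessarily large on the outcome scale; with a within-patient correlation of 0.75 it equals 0.55 raw SD.
- **That calling the sample 30 conceals a doubling of the data.** The arithmetic 15 × 2 is right and openly stated, nothing in the protocol analyses 30 independent observations, and step 5 shows that pairing can offset the smaller count. The fault is in the label.
- **That the 5% margin of error can be tested as the precision of a proportion, and fails.** The protocol does not say what the margin refers to and sets no proportion as its target, so such a calculation would describe nothing planned here.

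What remains is that the borrowed figures appear in this protocol only to justify its own size, and they cannot do that for a different comparison and procedure. A detailed analysis plan may exist separately, but it would not alter the justification printed in section 4.1.

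**Conclusion.** The point holds in a limited form. The 80% power and 5% margin of error are unsupported for bupivacaine versus ropivacaine in this trial, and the size is 15 paired differences from 30 sites, not a sample of 30.

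If the drugs are compared by a two-sided 5% paired t-test on all 15 patients, 80% power requires a true mean difference of about 0.78 SD of the within-patient differences, and the interval half-width is about 0.55 SD. The VAS translations rest on an assumed SD of 2 points, with 1.5 to 3 as the range. Whether the trial has adequate power for any of its outcomes cannot be decided from the protocol.

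**What to change.** In section 4.1 and the Summary:

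1. State the size as 15 patients, giving 15 paired differences from 30 surgical sites, chosen for convenience.
2. Remove the earlier study's 80% power and 5% margin of error as justification. The study may still be cited as the precedent for the number of patients.
3. State what 15 pairs deliver: a detectable mean difference of about 0.78 SD of the within-patient differences at 80% power (two-sided 5% paired t-test), and a 95% confidence interval half-width of about 0.55 SD. Name the outcome to which this is applied and, if it is translated into VAS points, label the SD as an assumption and give a range.
4. Say that a result without a significant difference is to be read with that interval, and not as coming from a trial with 80% power.

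The cost is wording only, with no extra patients. The drawback is that the stated basis for the size becomes less favourable.
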